The PI is a full-time scientific staff of ICDDR,B and has the experience of conducting randomized controlled trials of ARI vaccines in mothers and children. This project will occupy up to 50% 0f her time depending on the needs at different points during the trial. [name] is a microbiologist in charge of the ARI laboratory at ICDDR,B. [name] is a senior epidemiologist and has extensive experience in vaccine studies and will advise on the conduct of the trial and data analysis. [name] is an epidemiologist and Head, Child Health Programme will be helping in the data analysis. He has extensive experience in field studies.

A full-time physician will monitor the side-effects of the conjugate pneumococcal vaccine, which will be used for the first time in very young infants. Enrolled infants will have blood drawn from their veins on 4 occasions.

To save cost on local travel, the study team will be using public transport for follow-up home visits and not the ICDDR,B pool vehicles. International travel provisions are proposed for setting up the collaborative activities, data analysis and conference presentation.

The costs of microbiology and the immunology laboratories have been calculated. There will be about 1260 nasopharyngeal cultures done together with sensitivity and serotyping of pneumococcal strains. There will be 1260 blood samples from the study subjects. Pneumococcal antibodies i. e. measurements of total IgG, and specific subclass IgG₁ and IgG₂ will be done in individual samples. Functional antibodies will be done on selected samples. Serotype specific antibody assays will be conducted on 4 four vaccine types and 2 non-vaccine types.

Dissemination and Use of Findings:

Results of the study will be written up for publication in a peer reviewed journal and presented at International and Regional scientific conferences. We shall share the results of this investigation immediately with our collaborating investigators.

References:

- 1. JP Grant. The State of the World's Children 1995. UNICEF Report. Oxford University Press.

- 3. WHO/VRD/GEN/96.02. Review of immunization approaches to prevent diseases occurring in early childhood.
- 4. Shann F. Etiology of severe pneumonia in children in developing countries. Ped Infect Dis 1984; 5: 247-52.

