One hundred and eighty healthy pregnant women in their third trimester will be enrolled after informed consent. Each will be given a unique identification number, which will indicate the study group she is assigned to. The numbers assigned will be from a pre-prepared list of numbers. Randomization will be a one step block design of 4 to ensure that in each block the groups are equally represented. This will entail in the study groups will be randomised to the receiving the pneumococcal polysaccharide vaccine (study) and those in the control study groups meningococcal vaccine (25). All infants will receive the conjugate pneumococcal vaccine at 6, 10 and 14 weeks of age (Appendix 1). Both these polysaccharide vaccines have been shown to be safe in our hands in published studies in Dhaka (13,25)

The design ensures that timing of blood specimens is parallel in the 4 groups, so direct comparison of each intervention can be made. For purposes of masking, every mother receives an injection of either pneumococcal or meningococcal vaccine. As such there will be total masking from the point of safety and side effect reporting in infant immunization. The major outcome variable (antibody levels) will also be determined by a completely blinded procedure.

The single dose vaccine vials will have a study label group code 1, 2, 3,4. The study coordinator will release vaccine vials to the study field staff who will take them to the obstetric practices. After determining the study group to which the mother is allocated, the field staff will note the study group allocation on the mothers' enrollment form, and write the mother's name and subject number on the vaccine vial label, and the vial number and study group in the mother's data form. After administration of vaccine, the empty study vaccine and tetanus vaccine vials will be returned to the coordinator, who will separately record the subject numbers and study group assignment against the vial numbers. Similar procedures will be followed for the study vaccines administered to the infants. The person who generates the allocation codes will not participate in subject assignment to study groups, vaccine administration, outcome assessment or data analyses, so that these processes remain blinded.

Baseline data collection

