Vaccines: All vaccines in the study are US FDA licensed.

7- valent Conjugate pneumococcal vaccine (licensed in Feb 2000) is manufactured as a lyophilized preparation requiring reconstitution with saline aluminum phosphate diluent before use. Each 0.5 ml dose of reconstituted vaccine contains 2µg saccharide per serotype 4, 9V, 14, 18C, 19 F and 23F, and 4 µg of serotype 6B (20 µg total saccharide); approximately 20µg of CRM 197 protein; and 0.5 mg of aluminum phosphate. This is a licensed product (Pnevenar®)of Wyeth-Ayerst.

23 valent pneumococcal polysaccharide vaccine contains 25 µg of each polysaccharide type dissolved in isotonic saline solution containing 0.25% phenol as a preservative. It is a mixture of highly purified capsular polysaccharides from 23 most prevalent or invasive pneumococcal types of streptococcus pneumoniae. This is a product (PNEUMOVAX 23) of Wyeth-Ayerst.

The **meningococcal vaccine** contains purified capsular polysaccharides of groups A,C,Y AND W-135 50 mcg of polysaccharide of each serotype. It is a product (Menomune ®) of Connought, used world-wide.

Specimens

See Appendix 1 for the schedule of collection of specific specimens, which will be collected at the follow up observation visits at birth, 6, 10, 14, 18-20 weeks.

Blood (5 ml) will be collected from mothers before and one month after immunization, and at the time of delivery. Infant cord specimens will be obtained at the time at delivery and infant (2ml) sera will be collected at 6, 14, and 18 weeks..

Breast milk will be collected at delivery and at 1, 6 and 18 weeks after delivery

Specimen processing Blood specimens will be centrifuged to separate serum, which will be aliquoted and frozen at -20 C at ICDDR, B until antibody assays are carried out. Breast milk specimens will also be centrifuged and the supernatant aliquoted and frozen at -20 C at ICDDR, B until antibody assays is carried out. All specimens will be labeled with the subject number and a specimen number, and their position in storage boxes will be recorded in the specimen database.

Microbiological processing of nasopharyngeal specimens for colonization study. Nasopharyngeal cultures for pneumococci will be obtained from the infants at birth and at each visit at 6, 10, 14, 18 weeks.

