Antibody assay validity and variability: Because antibody titers are the principal outcomes of this studies, we have instituted procedures to ensure validity and to reduce the variability of antibody assays. The ELISA for pneumococcal antibody has been standardized using the CDC/WHO standard assay procedures and FDA reference serum by [name] at Johns Hopkins University. Interassay variability is now assessed by running a local control serum (89-1C) on each plate to measure day to day variations. During a recent study of pneumococcal immunization of adults with and without HIV infection the co-efficients of variation for serotypes 6B, 14, 18C, 19F, and 23F were 30%, 12%, 11%, 12%, 16%, respectively. These values were typical for variation as reported by other centers, including the observation that type 6B has greater variability than the remaining serotypes. The laboratory will receive the serum coded and thus they will remain blinded to the code assignments.

Data analysis (see appendix 2)

Sera with undetectable antibody will be assigned half the lower limit of detection for the purposes of calculating means. Because the distributions of antibody titers and of the increases in titer (post-immunization antibody level divided by pre-immunization antibody level) are likely to be positively skewed, the values will be log-transformed to approximate a normal distribution for statistical analyses. The antilogarithms of the means of the log-transformed values will be reported as geometric mean titers (GMT) or as geometric mean increases. Continuous variables will be compared between groups by two-sided T-test or Mann-Whitney U test within groups by the paired T-test, and associations of continuous variables will be assessed by Pearson's correlation coefficient or the Spearman rank correlation test. The Chi Square or Fisher's exact test will be used to compare proportions between groups.

The gestational age of the infants will be estimated by two methods. The mothers will be asked the date of the first day of their last menstrual period, from which we will calculate the duration of the gestation period. In addition, each child will be examined within 48 hours of birth using the method of Ballard to assess the neuromuscular and physical maturity of the infant (25). The Ballard technique assigns a score for neuromuscular and physical maturation and allows an estimation of gestational age.

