In order to determine the success of the randomization procedure, the following variables of the mothers and infants will be compared to determine if the means or proportions are significantly different between the groups: maternal age, height, education, and parity, household size, gestational age at immunization, gestational age at delivery, immunization-birth delivery, birth weight, percent of infants with birth weight less than 2.5 kg, and less than 37 weeks gestation. The geometric mean pneumococcal antibody titers before immunization and at the time of delivery will be compared between mothers in the study groups, by ANOVA. Similarly, the infants' antibody titers to pneumococcal polysaccharide, diphtheria toxoid and tetanus toxoid will be compared between the three study groups in cord, 6 week and 18 week specimens by ANOVA test. The groups will be compared with respect to key characteristics to assess randomization. Proportions with adverse events and proportions seroconverting will be compared using chi-square tests.

We will compare the final infant pneumococcal antibody GMT between study group 1 and 2 to assess the effect of passive antibody on the filial antibody response to three doses of glycoprotein conjugate pneumococcal vaccine.

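### Subject numbers, vial labels and specimen labels carry the study group, so the blinding the protocol claims is not supported by its own procedure, and the stated group count varies between two, three and four

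*Protocol*

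**What the plan says.** All places are in the Protocol.

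- **Subject number (Study Procedure):** "Each will be given a unique identification number, which will indicate the study group she is assigned to".
- **Vials (Study Procedure):** "The single dose vaccine vials will have a study label group code 1, 2, 3,4".
- **Field staff (Study Procedure):** once the group is determined, "the field staff will note the study group allocation on the mothers' enrollment form". They also write the group in the mother's data form.
- **Specimens (Specimen processing):** "All specimens will be labeled with the subject number and a specimen number".
- **Blinding claims:** Study Procedure says "The major outcome variable (antibody levels) will also be determined by a completely blinded procedure". Antibody assay validity and variability says "The laboratory will receive the serum coded and thus they will remain blinded to the code assignments".
- **Safeguard for assignment (Study Procedure):** "The person who generates the allocation codes will not participate in subject assignment to study groups, vaccine administration, outcome assessment or data analyses". The protocol concludes from this that those steps stay blinded.
- **Randomisation (Study Procedure):** a fixed block size of 4, stated in the text.
- **Number of groups:** Study Design, Sample size estimate and Appendix 1 describe two. Study Procedure refers to four groups and has four vial codes. Data analysis says infant titres "will be compared between the three study groups in cord, 6 week and 18 week specimens by ANOVA test", but then compares final titres between groups 1 and 2 only.

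**The concern.** A code protects blinding when it tells the holder nothing about which other participants share the same treatment. Here the group is built into the subject number, and the subject number is on the specimen. Anyone handling specimens can sort them into arms without knowing what the arms are.

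That matters at two points. First, the laboratory assays maternal sera taken before vaccination, one month after it and at delivery. Averaged over all mothers with one code, those results would show which code received pneumococcal vaccine. Values that look anomalous go back to the laboratory for review (Data management and quality control), and that judgement should be made without knowledge of arm. Second, safety is part of the primary objective, and reaction data are collected by study staff at home visits, while field staff have the group code on their forms.

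A shared code with a short fixed block also makes the next code partly predictable to enrolling staff. Finally, the differing group counts stand in the text from which the list, the labels and the analysis would be prepared.

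**Working it through.** **1. Sample size, to establish the intended number of arms.** Inputs: log10 means 0.559 and 0.258 (difference 0.301), SD 0.601 (Appendix 3); two-sided alpha 0.05, power 80%, 30% non-completion (Sample size estimate).

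n per group = 2 × (1.96 + 0.842)² × 0.601² / 0.301² ≈ 62.6, so 63. Power at 63 is 80.3%, matching Appendix 3. Enrolment is 63 / 0.7 = 90 per group, and 2 × 90 = 180. The stated 63, 90 and 180 reproduce and fit two arms.

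**2. The labelling chain.**

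| Step | As written | Consequence |
|---|---|---|
| Subject number | indicates group | the number carries the arm |
| Specimen label | subject number plus specimen number | the specimen carries the arm |
| Laboratory | receives coded serum | no separate laboratory code or relabelling is described |
| Vial and forms | shared group code, read and recorded by field staff | staff know who shares an arm |

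The one stated safeguard separates the person who generates the codes. It does nothing about what the codes reveal to those who use them. With two codes, breaking one gives the other by elimination, so all 180 women are unblinded. With four codes used equally, breaking one directly unblinds 180 / 4 = 45.

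**3. Predictability if staff see the whole sequence and the block boundaries.** Two arms in a block of 4 give six equally likely orders (AABB, ABAB, ABBA and their mirror images).

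- Certain in advance, positions 1 to 4: 0, 0, 1/3, 1. Mean = (4/3) / 4 = 33%.
- Best guess correct: 1/2, 2/3, 2/3, 1. Mean = (17/6) / 4 = 70.8%, against 50% by chance.

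**4. Predictability if three clinics share one list.** Assumptions: equal recruitment, so each earlier assignment is seen with probability 1/3; block positions known. If a and b earlier assignments of the two codes in the block have been seen, the best guess is right with probability max(2 − a, 2 − b) / (4 − a − b).

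- Certain: position 3, (1/9)(1/3) = 1/27; position 4, (6/27)(1/3) + 1/27 = 3/27. Mean = (4/27) / 4 = 3.7%.
- Best guess correct: 0.500, 0.556, 0.593, 0.630. Mean = 2.278 / 4 = 57%.

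**5. Predictability if all four vial codes are used once per block.** Certain: 1/4 = 25%. Best guess: (1/4 + 1/3 + 1/2 + 1) / 4 = 52.1%, against 25% by chance. This is prediction of the code, not of the vaccine.

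**6. Can assay results break the code during enrolment?** Tentative Time schedule: recruitment 08/02 to 02/03, laboratory assays 04/03 to 12/03. On that schedule they cannot.

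**The case against.** Several counter-arguments have force.

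- *The identifier may point to the group only through a look-up list, and coded serum may mean relabelled serum.* Both are possible. The labelling sentence concerns processing and storage in Dhaka, and sera are shipped later. But the protocol describes no relabelling, and its plain statement is that the number indicates the group. The gap stands.
- *The laboratory is said to be blind to what the codes mean, not to the codes themselves.* True on a narrow reading. It does not rescue the claim, because maternal titres grouped by code would reveal the meaning.
- *Uninformative numbers do not fully blind the laboratory.* Correct. Each mother-infant pair is assayed on one plate, so a maternal rise can suggest that pair's arm under any numbering. The change removes sorting by arm across the whole trial, not this pair-level inference.
- *The 33% and 71% are a worst case.* Correct. Recruitment is at three facilities and the protocol does not say whether they share a list, so a range is needed.
- *Predicting a code is not predicting a vaccine.* Correct, and the schedule rules out assay results as the route during enrolment. Some other breach would be needed.

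A reader might also infer that four arms of 45 women could be randomised, with a serious loss of power. The documents do not support this. There are two maternal vaccines, one infant schedule, 90 per group for a total of 180, and two groups in Appendix 1. The four codes could be two masked codes per vaccine, though the protocol does not say so, or text left over from another design.

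**Conclusion.** The point holds as a gap between the blinding claimed and the procedure written. Group-bearing subject numbers on specimens, and shared group codes on vials and forms, let specimens and participants be sorted by arm. The claims about the antibody outcome and the laboratory need a procedure that supports them.

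Predictability of the next code lies between about 4% certain with 57% guessable and 33% certain with 71% guessable, for two codes in fixed blocks of 4. The lower figures assume three equal clinics on one list with staff seeing only their own assignments; the upper figures assume full sight of the sequence. Both assume known block boundaries, and neither gives the vaccine unless the code is broken. A reader might infer that selection at enrolment or bias in the assays is established. It is not: no bias has been quantified, and the assays are standardised with a reference serum and plate controls.

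The sample size is unaffected. The differing group counts are a matter of consistency, but the four vial codes and the three-group ANOVA must be reconciled with two arms.

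**What to change.** Before enrolment:

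1. Use subject numbers that carry no group information.
2. Give each vial a unique number, matched to a subject number on a list held by the person who generates the codes. Put no group code on vials, enrolment or data forms, or specimen labels.
3. Send sera to the laboratory under separate specimen numbers, and say so where blinding is claimed.
4. Acknowledge that assaying mother and infant on one plate can still suggest a pair's arm, and word the blinding claim accordingly.
5. State two groups throughout: correct the four-group reference and vial codes 1 to 4 in Study Procedure, and the three-group comparison in Data analysis. If several codes per vaccine are intended, say so and say how they are pooled. With two groups, ANOVA and the equal-variance t-test are equivalent, so no analysis is lost.
6. Optionally, vary the block size.

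The cost is a new label format, a new list and edited text. The figures 63, 90 and 180 stay as they are, with no extra participants or staff.

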The nasopharyngeal swabs from the infants will be obtained in home or clinic using flexible Calgiswabs, immediately placed in Amies transport medium and shipped to the ICDDR, B microbiology laboratories and cultured on blood agar within 8 hours. We have standardized these procedures in Dhaka, and shown that pneumococci experimentally inoculated on Calgiswabs will survive for at least 2 days in local conditions in the Amies medium. The swabs will be inoculated in the laboratory on sheep blood agar with 0.5 g/ml gentamycin. Standard microbiological procedures will be used for identification and serotyping of *S. pneumoniae* isolates, using serotyping sera from Statens Seruminstitut, Copenhagen. Using these procedures, we have shown that up to 78% of Dhaka infants are colonized by pneumococci before 6 months of age.

Laboratory procedures assessment:

Sera and breast milk specimens will be separated, aliquoted, stored at -20° C at ICDDR,B and later shipped on dry ice for antibody assays. Serotype specific IgG and IgA (class and sub-class) antibodies to *S. pneumoniae* to 4 vaccine types, (1, 6, 19, 23) and 2 non-vaccine types, (2 and 42) will be assessed on serum and breast milk samples using the standard CDC/WHO standardized ELISA techniques) with minor modifications (27). Serum specimens from each mother-infant pair will be assayed together in a single plate. IgG1 and IgG2 antibodies to type 19F pneumococcal polysaccharide will be determined, if additional support for this purpose is obtained. The pneumococcal assays will be standardized against immune serum pool 89-SF ([name], Center for Biologics Evaluation and Research, FDA) with the following antibody assignments: 13.4 µg/ml of IgG and 0.5 µg/ml of IgA anti-pneumococcus type 6B, 9.1 µg/ml of IgG and 0.6 µg/ml of IgA anti-type 19F. For IgG subclass assays serum 89-SF will be assigned 100 ELISA Units/ml since no µg/ml assignment has been established. Diphtheria and tetanus toxoid IgG antibody estimations will be by ELISA using methodology similar to those for the pneumococcal assays (27).

Outcome measures for primary hypothesis

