We will test the hypothesis that conjugate pneumococcal vaccine reduces acquisition and carriage of pneumococci in infants. The main outcome measure will be the acquisition by the study children of specific pneumococcal serotypes (VT) contained in the vaccine (for 7 valent Lederle conjugate: groups/types 4, 6B, 9V, 14, 18C, 19F, 23F). The overall proportion of infants who acquire VT, the median age of acquisition, and median duration of carriage of VT will be compared between the study and control groups with appropriate statistical tests. Kaplan-Meier survival curves will be used to compare the cumulative proportions of children who acquire vaccine serotypes at each time point during this study. Bi-variate analyses will be carried out to determine the association of selected risk factors (breast feeding, crowding, etc) and the acquisition and carriage of VT and non-VT by study children. A multi-variable analysis will be done to determine the independent effects of these risk factors. The association of carriage of drug resistant pneumococci with risk factors will similarly be analyzed with bivariate and multivariable analyses. The data on carriage of pneumococci will be analyzed to determine if established carriage of VT pneumococci is shortened or otherwise influenced by the receipt of pneumococcal vaccine. If carriage of VT is reduced in recipients of pneumococcal vaccine, it will be of interest to determine if carriage of non-VT but pathogenic serotypes (types 7, 15) is increased in vaccinees, if there are adequate numbers of isolates of these types.

The association of specific serum IgG and IgA antibodies to the commonly carried pneumococcal types 6, 19, 14 and 23 with carriage of these types will be examined by chi square and regression techniques, to determine if there is an statistical association, and if there is a specific level of serum antibody which predicts reduction of carriage. We will also compare mean serum antibody titers for the most common colonizing serotypes between colonized and non-colonized infants. In mothers

who breast feed their infants, mean breast milk antibody titers against common serotypes will be compared in colonized and non-colonized infants (Appendix1)

Ethical issues

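### The antibody panel includes type 1, which is not in the infant conjugate vaccine, and leaves out type 14, which the planned antibody–carriage analysis needs

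*Protocol*

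**What the plan says.** *Laboratory procedures assessment* fixes the assay list: serotype-specific IgG and IgA antibodies "to 4 vaccine types, (1, 6, 19, 23) and 2 non-vaccine types, (2 and 42) will be assessed", in serum and in breast milk. *Budget Justification* repeats the count without naming the types: "Serotype specific antibody assays will be conducted on 4 four vaccine types and 2 non-vaccine types".

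*Vaccines* gives the composition of the infant vaccine: "2µg saccharide per serotype 4, 9V, 14, 18C, 19 F and 23F, and 4 µg of serotype 6B". The carriage part of *Data analysis* defines vaccine types by the same seven: "for 7 valent Lederle conjugate: groups/types 4, 6B, 9V, 14, 18C, 19F, 23F". The 23 types in the maternal polysaccharide vaccine are not listed anywhere.

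Two parts of the plan draw on the panel. *Outcome measures for primary hypothesis* treats infant antibody at 18 weeks, after three doses, as the active response, but does not name the serotypes. The carriage part of *Data analysis* says that the link between serum IgG and IgA "antibodies to the commonly carried pneumococcal types 6, 19, 14 and 23 with carriage of these types will be examined".

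**The concern.** The assay list does not fit the vaccine or the analyses that depend on it.

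**Type 1.** Infants receive no type 1 antigen from the conjugate. Whatever type 1 antibody they have at 18 weeks is maternal antibody that has not yet decayed, or comes from natural exposure. Two planned analyses could mislead if type 1 is treated like the other vaccine types:

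- *Comparison of final GMT between groups 1 and 2.* The Background reports infant antibody above 0.15 µg/ml up to 22 weeks of age after maternal immunization, which is later than the 18-week sample. If the maternal vaccine contains type 1, leftover passive antibody could raise the type 1 GMT, and the share above 0.15 µg/ml listed in Appendix 2, in group 2. Under a vaccine-type label this could pass for a better response to the conjugate.
- *Correlation of cord titer with 18-week titer.* The plan reads a negative correlation as inhibition. With no active response to inhibit, the 18-week type 1 titer would tend to rise with the cord titer. The absence of a negative correlation would then say nothing about inhibition.

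**Type 14.** It is in the conjugate and is named for the carriage analysis, but no section plans to measure it in this trial. That analysis cannot be run from the data the plan would produce.

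**Working it through.** No model is needed; the lists can be set side by side. Types are matched at group level (6 with 6B, 19 with 19F, 23 with 23F), because the panel gives no subtype letters.

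| List | Types | Source in the Protocol |
|---|---|---|
| Panel, called vaccine types | 1, 6, 19, 23 | Laboratory procedures assessment |
| Panel, called non-vaccine types | 2, 42 | Laboratory procedures assessment |
| Infant conjugate | 4, 6B, 9V, 14, 18C, 19F, 23F | Vaccines; Data analysis (carriage) |
| Needed for antibody–carriage analysis | 6, 14, 19, 23 | Data analysis (carriage) |

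**Step 1: the plan's count of four vaccine types.** The overlap of {1, 6, 19, 23} with the conjugate list is {6, 19, 23}. That is 3 of 4, so the stated count is not reproduced against the conjugate. The one left over is type 1.

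**Step 2: types needed for carriage but not assayed.** {6, 14, 19, 23} minus {1, 6, 19, 23, 2, 42} leaves {14}, which is 1 of 4.

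**Step 3: the panel with type 14 in place of type 1.** {6, 14, 19, 23} gives 4 of 4 in the conjugate and 4 of 4 of the types needed for carriage. The assay count stays at four plus two.

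**Step 4: could the conjugate list be incomplete?** The listed amounts add to 6 × 2 + 4 = 16 µg, while the same sentence gives a total of 20 µg. Those figures need reconciling in their own right. They do not make room for type 1: the product is described as 7-valent, seven types are named, and two sections name the same seven.

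**Step 5: does the sample size depend on the panel?** Appendix 3 uses log means of 0.559 and 0.258 and an SD of 0.601, so d = 0.301. With n per group = 2(z₁ + z₂)² × SD² / d²:

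- SD²/d² = 0.3612 / 0.0906 = 3.987.
- Two-sided 5%, 80% power: 2 × (1.960 + 0.842)² × 3.987 = 2 × 7.849 × 3.987 = 62.6, so 63.
- One-sided 5%: 2 × (1.645 + 0.842)² × 3.987 = 2 × 6.183 × 3.987 = 49.3, so 50.

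Both agree with Table 2. The starting GMT of 3.6 µg/ml is the 19F value in Table 1, so neither type 1 nor type 14 enters the calculation.

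**The case against.** The strongest defence is that the label on the panel may refer to the maternal 23-valent vaccine. The panel covers maternal serum and milk as well as infant serum, and the definition of vaccine types in *Data analysis* is written for the carriage outcome. Because the 23 types are not listed, this reading can be neither confirmed nor excluded, and the label itself cannot be called wrong with certainty. That much stands. It does not help the infant analyses: type 1 still cannot measure a response to the conjugate, and type 14 is still missing.

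Type 1 may also be useful. *Data analysis* plans to calculate natural antibody decay. If the maternal vaccine contains type 1, its titers would follow transferred antibody to 18 weeks without boosting, which types 6, 19 and 23 cannot do once the conjugate doses begin. This stands as a reason to consider keeping it, outside the conjugate analyses.

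A reader might infer that one of four primary results is void, or that type 1 will be reported as conjugate immunogenicity. The Protocol supports neither. The primary outcome does not name its serotypes, and the panel openly includes two types labelled non-vaccine, so being on the panel does not make a type a primary endpoint. The misreading is a risk that the text leaves open, not a stated plan.

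A reader might also object that only 3 of the 7 conjugate serotypes are assayed. The opening project summary promises only selected serotypes, so omitting 4, 9V and 18C is not an error. Type 14 differs because a planned analysis names it.

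**Conclusion.** This is an internal inconsistency that should be corrected before assays start. Followed as written, one of the four types called vaccine types cannot show the infant response to the conjugate, and one of the four named antibody–carriage analyses under secondary objective 4 has no titers.

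The reach is limited. Types 6, 19 and 23 can still address the primary question and their own carriage analyses. The gap is also still reversible: specimens are to be aliquoted and frozen, and the time schedule places laboratory assays after infant follow-up. It would be too strong to say that the type 14 analysis is lost; that is so only if the list stays as it is.

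The conclusion assumes that the seven listed serotypes are the full content of the conjugate and that the laboratory list is complete. It does not depend on what the maternal vaccine contains.

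**What to change.** Reconcile *Laboratory procedures assessment*, the carriage part of *Data analysis* and *Budget Justification* to one named panel, with subtypes, that includes type 14. Two ways stay within the budgeted four plus two assays:

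1. Put type 14 in place of type 1, so that the vaccine types are 6B, 14, 19F and 23F, with 2 and 42 as non-vaccine types.
2. Use the same four vaccine types and keep type 1 in one of the two non-conjugate slots.

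In either case, state that vaccine type means the conjugate serotypes. If type 1 is kept, exclude it from every analysis of conjugate response or inhibition, and use it only as a marker of transferred antibody, provided the maternal vaccine is confirmed to contain it.

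The first option gives up a possible unboosted marker of passive antibody decay. The second gives up type 2 or type 42. The number of assays does not change. The laboratory has run type 14 before: *Antibody assay validity and variability* reports that the "co-efficients of variation for serotypes 6B, 14, 18C, 19F, and 23F were" 30%, 12%, 11%, 12% and 16% in that order, so 12% for type 14, and gives no figure for type 1. Those data come from a study of adults, so performance in infant serum and breast milk, and the cost per assay, would still need to be confirmed.
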